## 6.11 Safety Analyses

Safety analyses will be presented by the treatment received for the Safety Analysis Set.

### 6.11.1 Adverse Events

AEs will be collected from the date of informed consent until completion of the end-of-study visit.

A treatment emergent adverse event (TEAE) is defined as:

- Any AE that has an onset on or after the first dose of study drug through completion of the end-of-study visit.
- Any pre-existing AE that has worsened in severity on or after the first dose of study drug through completion of the end-of-study visit.

AEs occurring prior to first dose are considered non-treatment emergent and will be listed only.

Relationship of the AE to treatment can be recorded as Not Related, Unlikely, Possible, Probable or Certain. A treatment-related AE is defined as any AE classified as possibly, probably or

QMD Ref: Worldwide-TMP-ST-006-4.0 Effective: 12Aug2019	Governing QMD: Worldwide-SOP-ST-001
Confidentiality Statement	

This document is the property of Worldwide Clinical Trials Inc. and may not be duplicated, copied, altered or removed from company without prior approval from Worldwide Quality Assurance or in compliance with Worldwide Standard Operating Procedures.

Worldwide Clinical Trials Controlled Quality Management Document		
 WORLDWIDE CLINICAL TRIALS	Sponsor:	Global Alliance for TB Drug Development
	Protocol Number:	TBAJ-876-CL001
STATISTICAL ANALYSIS PLAN – PHASE 1		

certainly related to the study drug. If an AE has missing relationship it is assumed to be related to the study drug for analysis purposes.

Severity of the AE will be graded using the Division of Microbiology and Infectious Disease (DMID) Toxicity Grade November 2007 version: Grade 1 (Mild), Grade 2 (Moderate), Grade 3 (Severe), Grade 4 (Potentially Life-Threatening). Maximum grade will be assumed for an AE with missing grade.

An overall summary of TEAEs (incidence and number of events) will be presented by treatment group and overall, for the following:

- Any TEAE
- Any Treatment-Related TEAE
- Any Serious TEAE
- Any Serious Treatment-Related TEAE
- Any TEAE Leading to Early Discontinuation from Study
- Any TEAE Leading to Withdrawal of Study Drug (MAD only)
- Any TEAE Leading to Death

Summaries of TEAEs (incidence and number of events) will be presented by system organ class and preferred term, by treatment group and overall, for the following:

- TEAEs
- Treatment-Related TEAEs
- TEAEs by Maximum Severity (incidence only)
- TEAEs by Nearest Relationship (incidence only)

The following listings of TEAEs will be presented in Appendix 14.3.2 of the CSR.

- TEAEs Leading to Early Discontinuation from Study, Listing
- TEAEs Leading to Withdrawal of Study Drug, Listing (MAD only)
- Serious TEAEs, Listing
- Deaths, Listing

In addition, a listing of all reported AEs will be provided in Appendix 16.2.7 of the CSR.

System organ class will be presented in descending order of overall frequency and then alphabetically. Preferred terms will be displayed in descending order of overall frequency and then alphabetically.

QMD Ref: Worldwide-TMP-ST-006-4.0 Effective: 12Aug2019	Governing QMD: Worldwide-SOP-ST-001
Confidentiality Statement	

This document is the property of Worldwide Clinical Trials Inc. and may not be duplicated, copied, altered or removed from company without prior approval from Worldwide Quality Assurance or in compliance with Worldwide Standard Operating Procedures.

Worldwide Clinical Trials Controlled Quality Management Document		
 WORLDWIDE CLINICAL TRIALS	Sponsor:	Global Alliance for TB Drug Development
	Protocol Number:	TBAJ-876-CL001
STATISTICAL ANALYSIS PLAN – PHASE 1		

In counting the number of AEs reported, a continuous event (i.e. reported more than once and which did not cease), will be counted only once; a non-continuous AE reported several times by the same patient will be counted as multiple events.

For summary by severity, patients reporting more than one AE per system organ class and preferred term will only be counted once for the most severe event.

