1.6 Potential Adverse Effects in Human Subjects

Based on the nonclinical safety studies, human subjects should be monitored for the following potential effects:

- Myocardial damage (seen in dogs) by way of clinical chemistry biomarkers
- Skeletal muscle myopathy (seen in rats) by way of clinical chemistry biomarkers and clinical signs of muscle pain or weakness
- Damage to the stomach mucosa (seen in both species) by way of clinical signs of nausea, vomiting, or dyspepsia
- Diarrhea (seen in both species)
- Liver injury, both hepatocellular and biliary (seen in both species) by way of clinical chemistry biomarkers
- Effects on hematopoiesis (seen in dogs) by way of hematology analyses
- Effects on the pancreas (seen in dogs) by way of clinical chemistry biomarkers

In animals, all of these effects were reversible when dosing stopped, and they are expected to be so in humans, too, if they occur.

No studies have been done to evaluate the potential effects of TBAJ-876 reproductive function in male animals. The following side effects were noted in adult subjects/patients in studies of a similar drug in this class (bedaquiline - marketed as SirturoTM): nausea, tiredness, headache, vomiting, dizziness, diarrhea, liver injury, heart problems; prolongation of QTc interval, and pancreas injury.²

Clinical Safety Evaluation (Single Ascending Dose)

In the SAD part of TBAJ-876 CL-001, 47 healthy volunteers aged 20 to 50 years were dosed with a single dose of TBAJ-876 or placebo and followed up to Week 4 (Cohorts 1 through 3) or up to Week 10 (Cohorts 4 through 6) after dosing. Each cohort enrolled 8 subjects (6 randomized to active treatment and 2 to placebo), except for Cohort 4, which enrolled only 7 subjects. Review of the blinded safety data showed that TBAJ-876 was generally safe and well tolerated at doses between 10 mg and 400 mg. There were no serious or severe AEs. Most of the AEs were mild and all resolved.

AEs of interest, based on preclinical findings, included myocardial damage, skeletal muscle injury, gastrointestinal irritation, elevated pancreatic enzymes, elevated liver enzymes, and cytopenia.

1) There were 3 subjects with elevated lipase (1 in the 10 mg cohort, and 2 in the 50 mg cohort) and 1 with elevated amylase (50 mg), who also had an elevated lipase. These laboratory abnormalities were not associated with any symptoms and resolved completely.

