2 OBJECTIVE

The primary objective of the study is:

 To evaluate the safety and tolerability of single and multiple ascending doses of TBAJ-876 oral suspension, and single doses of two strengths of TBAJ-876 tablets in healthy subjects.

The secondary objectives of the study are:

- To determine the pharmacokinetics (PK) of TBAJ-876 and its metabolites (M2 and M3) after single and multiple doses of TBAJ-876 oral suspension, and single doses of two strengths of TBAJ-876 tablets in healthy adult subjects.
- To compare the rate and extent of absorption of a single oral dose of TBAJ-876 oral suspension and two strengths of TBAJ-876 tablets when administered after a high-calorie, high-fat meal versus when it is administered fasting in healthy adult subjects.
 - To compare the rate and extent of absorption of the 4 x 25 mg tablets and the 1 x 100 mg tablet under fasted conditions.
 - To compare the rate and extent of absorption of a single oral dose of 100 mg of the TBAJ-876 oral suspension and two strengths of TBAJ-876 tablets under fed and/or fasted conditions.

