Subjects will check-in to the clinic on Day -1 and be confined through Day 8. Subjects will be discharged from the clinic on Day 8. Subjects will return for one follow-up visit on Day 14 for PK and safety. Subjects will receive a follow-up phone call on Day 21. Subjects will complete the procedures specified for those study days only. All ECGs performed in Cohort 7 will be triplicate ECGs at each time point.

In addition, subjects will have triplicate ECGs at 16 hours postdose.

Additional cohorts may be enrolled if deemed appropriate by the Sponsor to repeat a dose level, to study another dose level, or to increase cohort size (subject numbers). The number and timing of PK sampling and safety assessments may be further revised based on what is learned based on evolving data PK information.

These decisions concerning additional cohorts will not take place until the Sponsor, in conjunction with the Principal Investigator, has determined that adequate safety, tolerability, and PK from the previous cohorts have been demonstrated. The Institutional Review Board (IRB) should be immediately notified of this revised approach.

During each cohort, blood samples will be obtained before each dose of study drug, and at serial timepoints postdose on Days 1-8, 10, 14, 17, 21, and 28. Plasma PK samples will be analyzed for TBAJ-876, M2, and M3 using validated analytical methods. Appropriate PK parameters will be calculated using non-compartmental methods.

In addition, blood and urine will be collected for clinical laboratory evaluations.

Female subjects will have blood collected for serum pregnancy testing. Females claiming postmenopausal status will have blood collected to measure follicle-stimulating hormone (FSH) levels.

Table 6 presents the planned 6 dose cohorts and the additional Cohort 7 for Part 1 of the study.

Table 6 Single Ascending Dose Cohorts, Part 1

Cohort (Dose Level) ^a	Dose ^c	
1 (sentinel group) ^b	Single dose of 10 mg TBAJ-876 (n=2)	Placebo (n=1)
1 (remainder of cohort) ^b	Single dose of 10 mg TBAJ-876 (n=4)	Placebo (n=1)
2	Single dose of 25 mg TBAJ-876 (n=6)	Placebo (n=2)
3	Single dose of 50 mg TBAJ-876 (n=6)	Placebo (n=2)
4	Single dose of 100 mg TBAJ-876 (n=6)	Placebo (n=2)
5	Single dose of 200 mg TBAJ-876 (n=6)	Placebo (n=2)
6	Single dose of 400 mg TBAJ-876) (n=6)	Placebo (n=2)
7	Single dose of 800 mg TBAJ-876 (n=6)	Placebo (n=2)

mg = milligram; n = number of subjects.

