6.4 Confinement

For Part 1, subjects will be admitted to the research center on Day -1 and remain in the research center until completion of the procedures on Day 8. Subjects will return for subsequent follow up visits on Days 10, 14, 17, 21, and 28. Available subjects from

Cohorts 4 and 5, and all subjects in Cohort 6 will also return bi-weekly (+/- 2 days) up to 10 weeks or longer postdose.

Additional cohort, Cohort 7: Subjects will check-in to the clinic on Day -1 and be confined through Day 8. Subjects will be discharged from the clinic on Day 8. Subjects will return for one follow-up visit on Day 14 for PK and safety. Subjects will receive a follow-up phone call on Day 21.

For Part 2, subjects will be admitted to the research center on the evening of Day -1 and remain in the research center until completion of the procedures on Day 21. Subjects will return for subsequent follow up visits on Days 42, 63, 84, 105, and 126 (+/- 1 day) and will receive a phone call on Day 133 (+/- 1 day).

For Part 3, subjects will be admitted to the research center on the evening of Day -1 and remain in the research center until completion of the procedures on Day 8. Subjects will return for subsequent follow-up visits on Days 10 and 14 and will receive a follow-up phone call on Day 21.

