PK blood collection ⁱ			X	X	X		X	X	X	X	X		X	X	X	X	X	X	X		X	X	X		X	X	X	X	X	X	X	X	X	X
Cardiac Telemetry; 12 – lead Holter monitoring ^j			X	X	X	X	X	X	X	X	X	X	X	X	X	X	X	X																
ECG extractions from Holter recording ^k			X	X	X	X	X	X	X	X	X	X	X		X			X																

CI = check-in; ECG = electrocardiogram; FSH = follicle-stimulating hormone; FU = follow up; HIV = human immunodeficiency virus; N/A = not applicable; PK = pharmacokinetic; SCR = screening; T and R = temperature and respirations

- * Available subjects from Cohorts 4 and 5, and all subjects in Cohort 6 will return bi-weekly (+/- 2 days) up to 10 weeks postdose. Subjects will complete the same procedures as required for Day 28 at each visit.
- ** Subjects in Cohort 7 will be discharged from the clinic on Day 8. Subjects will return for one follow-up visit on Day 14 for PK and safety. Subjects will receive a follow-up phone call on Day 21. Subjects will complete the procedures specified for those study days only.
- a. The 16-hour time point following dosing on Day 1 will either be on Day 1 or Day 2, depending upon time of dosing on Day 1.
- b. Heart Murmur: Presence of heart murmur
- c. Vital signs (blood pressure, pule rate, temperature, respiration rate, and pulse oximetry) will be measured at screening and check-in (Day-1). Vitals signs will be measured within 90 minutes prior to dosing and within 15 minutes of the defined time points. Both blood pressure and pulse rate should be captured simultaneously. Blood pressure and pulse rate will be measured after subjects are in a seated position for at least 2 minutes and then again after standing for 1 minute, except when they are supine or semi-reclined because of study procedures and/or AEs, or as deemed necessary by the Investigator.
- d. 12-lead safety ECGs will be printed and reviewed on-site by the Principal Investigator or designee. Triplicate ECGs will be completed at screening, Day -1, at 48 hours and on Day 8 or upon early withdrawal only. All other time points will be single ECG readings within 15 minutes of the time points. The first ECG Day 1 may be done within 2 hours prior to dosing and must be completed 20 minutes prior to the predose blood draw. All safety ECGs on Day 1 and Day 2 will be extracted from a continuous 12 lead Holter recording at discrete

Global Alliance for TB Drug Development

CONFIDENTIAL

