## 6.2.11 Concentration-Time Data

Blood Samples for PK analysis in plasma will be collected at:

Part 1 (SAD):

- Predose, and 0.5, 1, 2, 3, 4, 5, 6, 8, 10, 12, 16, 20, 24, 28, 32, 36, 40, 44, 48, 54, 60, 66, 72, 80, 88, 96, 120, 144, and 168 hours after dosing, then on Days 10, 14, 17, 21 and 28.

Additional samples will be drawn on Days 42, 56, and 70 for Cohorts 4, 5, and 6.

- For Cohort 7, PK samples will be collected at predose (0), and 0.5, 1, 2, 3, 4, 5, 6, 8, 10, 12, 16, 20, 24, 28, 32, 36, 40, 44, 48, 54, 60, 66, 72, 80, 88, 96, 120, 144, and 168 hours (Day 14) after dosing.

Part 1 (FE):

- Predose, and 0.5, 1, 2, 3, 4, 5, 6, 8, 10, 12, 16, 20, 24, 28, 32, 36, 40, 44, 48, 54, 60, 66, 72, 80, 88, 96, 120, 144, and 168 hours after dosing, then on Days 10, 14, 17, 21 and 28.

Part 2 (MAD):

- Day 1: Predose, and 0.5, 1, 2, 3, 4, 5, 6, 8, 10, 12, 16, 20, 24 (pre-dose sample for Day 2).

QMD Ref: Worldwide-TMP-ST-006-4.0 Effective: 12Aug2019	Governing QMD: Worldwide-SOP-ST-001
Confidentiality Statement	

This document is the property of Worldwide Clinical Trials Inc. and may not be duplicated, copied, altered or removed from company without prior approval from Worldwide Quality Assurance or in compliance with Worldwide Standard Operating Procedures.

Worldwide Clinical Trials Controlled Quality Management Document		
 WORLDWIDE CLINICAL TRIALS	Sponsor:	Global Alliance for TB Drug Development
	Protocol Number:	TBAJ-876-CL001
STATISTICAL ANALYSIS PLAN – PHASE 1		

- Day 14: 0.5, 1, 2, 3, 4, 5, 8, 12, 16, 20, 24, 28, 32, 36, 40, 44, 48, 54, 60, 66, 72, 80, 88, 96, 120, 144, and 168 hours after dosing and on Days 42, 63, 84, 105, and 126.
- Additional or fewer samples may be collected at times to be determined based on the results from previous cohorts. Predose trough concentrations will be collected daily from Days 2 through 13.

Part 3 (RBA and FE):

- Pre-dose, and 0.5, 1, 2, 3, 4, 5, 6, 8, 10, 12, 16, 20, 24, 28, 32, 36, 40, 44, 48, 54, 60, 66, 72, 80, 88, 96, 120, 144, and 168 hours after dosing, then on Days 10 (240 h) and 14 (336 h).

Concentration-time data will be tabulated by part, nominal time, analyte, cohort (group for Part 3), and study day (for Part 2) using descriptive statistics. For presentation of the individual data and summary statistics, concentrations below the limit of quantitation (BLQ) will be set to zero.

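### The Part 1 TEAE tables set dose columns side by side over unequal observation times, shortest at 800 mg, with no common window or person-time

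*SAP*

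**What the plan says.** The primary objective (Protocol 2) begins "To evaluate the safety and tolerability of single and multiple ascending doses of TBAJ-876 oral suspension". Its main display is the set of TEAE tables in SAP 6.11.1: "An overall summary of TEAEs (incidence and number of events) will be presented by treatment group and overall, for the following". A TEAE is an event that starts or worsens from first dose until the end-of-study visit is complete. SAP 6.3 gives Part 1 one column per dose, with 100 mg split into fasted and fed, and one placebo column pooled over cohorts. I found no common window, event rate or summary of follow-up time for Part 1. The only duration summary (SAP 6.9) is dosing duration in Part 2.

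Follow-up is not the same in every column:

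- **Cohorts 1-6.** Protocol 1.6 describes subjects as "followed up to Week 4 (Cohorts 1 through 3) or up to Week 10 (Cohorts 4 through 6) after dosing".
- **Cohorts 4-6, extra visits.** Table 15 states "Available subjects from Cohorts 4 and 5, and all subjects in Cohort 6 will return bi-weekly (+/- 2 days) up to 10 weeks postdose", and then "Subjects will complete the same procedures as required for Day 28 at each visit". The AE row of that table covers Day 28. SAP 6.2.11 dates the extra visits: "Additional samples will be drawn on Days 42, 56, and 70 for Cohorts 4, 5, and 6".
- **Cohort 7 (800 mg).** Protocol 3 states "Subjects will return for one follow-up visit on Day 14 for PK and safety", followed by a telephone call on Day 21.
- **Food-effect cohort.** SAP 6.2.11 schedules sampling to Day 28.

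**The concern.** Crude incidence rises with time observed, even when the drug does nothing. The highest single dose is observed for the shortest time, so the lean in the table is toward reassurance at the dose where reassurance matters most. The pooled placebo column has a longer average observation time than the 800 mg column, so active against placebo at 800 mg is affected in the same direction.

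Laboratory findings add a second route. Protocol 7.7 makes every laboratory change of Grade 2 or above an AE, so the count also depends on how often blood is drawn, and Cohort 7 has the fewest draws.

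**Working it through.** The plan states no figure on this point, so there is none to reproduce. The check compares expected incidence when the AE rate is the same in every column.

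**Where each window ends.** SAP 6.11.1 closes the window at the end-of-study visit. Table 8 and Table 15 footnote f place end of study at Day 28, and Table 8 gives the 10-week follow-up its own row. Yet Cohorts 4-6 go on having visits with AE collection after Day 28, and no passage labels an end-of-study visit for Cohort 7. The synopsis gives Part 1 about 56 days from Day -1 to exit, which matches neither. Two readings are open:

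- *Reading A:* Day 28 ends Cohorts 1-6 and the food-effect cohort; Day 14 ends Cohort 7.
- *Reading B:* the 10-week visits and the Day 21 call count: 28 days (Cohorts 1-3, food effect), nominally 70 days (Cohorts 4-6), 21 days (Cohort 7).

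**Formula.** P(at least one TEAE) = 1 - exp(-rate x days/7). The rate is an assumption, not in the documents: 3%, 5% or 10% per subject-week, constant and equal in all columns. Expected subjects = 6 x P, for six active subjects per cohort.

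*Reading A, 28 days against 14 days (800 mg)*

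| Rate per week | 28 days | 14 days | Ratio | Subjects of 6 |
|---|---|---|---|---|
| 3% | 11.3% | 5.8% | 1.9 | 0.68 vs 0.35 |
| 5% | 18.1% | 9.5% | 1.9 | 1.09 vs 0.57 |
| 10% | 33.0% | 18.1% | 1.8 | 1.98 vs 1.09 |

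The largest gap is 1.98 - 1.09 = 0.89 of a subject. Event counts scale as 28/14 = 2.

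*Reading B, 70 days (400 mg) against 21 days (800 mg)*

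| Rate per week | 70 days | 21 days | Ratio | Subjects of 6 |
|---|---|---|---|---|
| 3% | 25.9% | 8.6% | 3.0 | 1.56 vs 0.52 |
| 5% | 39.3% | 13.9% | 2.8 | 2.36 vs 0.84 |
| 10% | 63.2% | 25.9% | 2.4 | 3.79 vs 1.56 |

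Event counts scale as 70/21 = 3.3.

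**Pooled placebo (two planned per cohort, 14 in all).** Reading A: (12 x 28 + 2 x 14)/14 = 26 days, against 14 for 800 mg active. Reading B: (6 x 28 + 6 x 70 + 2 x 21)/14 = 45 days, against 21.

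**100 mg columns.** Reading A: 28 days, fasted and fed. Reading B: fasted (6 x 70 + 3 x 28)/9 = 56 days if all six Cohort 4 active subjects return, against 28 fed. Only available subjects of Cohorts 4 and 5 return. If three of six do, that cohort averages (3 x 70 + 3 x 28)/6 = 49 days.

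**Postdose safety laboratory draws (Table 8, Table 15 footnote e).** Cohorts 1-3: 6 h, 48 h, Days 5, 7, 10, 14, 17, 21, 28 = 9. Cohorts 4-6: 9 + 3 = 12 on the SAP sampling days, or 9 + 5 = 14 on the Table 8 volume budget. Cohort 7: 6 h, 48 h, Days 5, 7, 14 = 5. Through Day 14 the counts are 6 for Cohorts 1-6 and 5 for Cohort 7; through Day 21 they are 8 and 5.

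**The case against.** A reader might infer that the whole dose-tolerability picture is confounded with observation time: more AEs at 100-400 mg than at 10-50 mg, a distorted fed/fasted contrast, and 400 mg showing two and a half to three times the incidence at 800 mg. The documents do not support stating that as fact. All of it needs Reading B, and following subjects to Week 10 does not show that their late events enter the TEAE tables. On Reading A, Cohorts 1-6 and the food-effect groups share a 28-day window. Only the 800 mg and pooled placebo columns are out of line, and the gap is under one subject in six.

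The constant rate is also generous to the concern. Table 15 schedules AE inquiry densely through Day 8, in all cohorts alike, and only at scattered visits afterwards. Recorded AEs will lean toward that shared period, which pulls both ratios toward 1.

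Nor do the unequal windows reach the escalation decisions, which rest on about 14 days of safety data (Protocol 3.1). The tables are descriptive, no between-dose test is planned, and the study is not formally powered. Laboratory, vital-sign and ECG summaries are by visit, and every AE is listed.

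These arguments limit the size; they do not remove the point. On either reading 800 mg is observed for the shortest time, and no planned TEAE table shows time at risk. Late events cannot be assumed absent: Protocol 3 assumes a half-life of about 7 days and ties the length of follow-up to interim PK. By-visit summaries and listings let a reader rebuild a like-for-like count, but they do not correct the tables.

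**Conclusion.** The point holds, at modest severity. Part 1 cohorts are observed for different lengths of time, the 800 mg cohort for the shortest, and SAP 6.11.1 tabulates crude incidence and counts with nothing to offset this. The descriptive display is biased toward making 800 mg look better tolerated.

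The documents do not settle the size, because they do not say which visit ends the study for Cohorts 4-7. On Reading A the incidence ratio is about 1.8-1.9, and only the 800 mg and pooled placebo columns are affected. On Reading B the 400 mg to 800 mg ratio is about 2.4-3.0, and the 100-400 mg, fed/fasted and placebo columns are affected too. Both ranges assume equal constant rates of 3-10% per subject-week and are upper-end illustrations, given the concentration of AE inquiry in the first 8 days. No formal inference is invalidated.

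**What to change.** In SAP 6.11.1:

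1. State the day or visit that ends the TEAE window for each Part 1 cohort, including whether the visits after Day 28 (Cohorts 4-6) and the Day 21 call (Cohort 7) fall inside it.
2. Keep the whole-follow-up TEAE tables, so that late events stay in the main display, and add subject-weeks of observation and events per subject-week for each column.
3. Add Part 1 versions of Tables 14.3.1.1 to 14.3.1.5 restricted to onset within a window common to all cohorts. Day 21 is the last contact shared by all. Day 14 is the last shared clinic visit and the better choice for laboratory AEs, since draws are then nearly level (6 against 5, rather than 8 against 5 through Day 21).
4. Base statements comparing doses, fed with fasted, and active with placebo on the common-window tables.

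The cost is a date filter, a person-time row and one extra set of AE tables. Nothing in the conduct of the study changes.
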